6.2 Randomization

No randomization was planned for this study as it was a non-comparative study.

6.3 Interim Analysis

No interim analyses were planned for this study.

7. Statistical Analysis

7.1 General

Smith & Nephew's Global Biostatistics group will conduct the statistical analysis for this study. Unless otherwise stated, all significance tests and hypothesis testing will be two-sided, performed at the 5% significance level. Resulting p-values will be quoted and 95% two-sided confidence intervals will be generated where appropriate. All p-values will be rounded to three decimal places, p-values less than 0.001 will be presented as '<0.001' in all tables.

Where data summaries are specified, categorical and ordinal variables will be summarized with frequencies and percentages. Continuous variables will be summarized with the following summary

CONFIDENTIAL AND PROPRIETARY

This document contains information that is confidential and proprietary to Smith & Nephew PLC and Smith & Nephew, Inc. and is intended for use only by Smith & Nephew and its manufacturer. It shall not be reproduced or copied in whole or in part, nor shall the contents be disclosed by any means without prior written permission from Smith & Nephew, nor shall anyone make any use of it that is contrary to the expressed or implied wishes of Smith & Nephew

Statistical Analysis Plan	Smith+Nephew
A Prospective, Non-randomized, Multi-Center Investigation of All-suture-based Repair of Horizontal Meniscal Tears (STITCH Study)	Number: CTX-CP001
	Version: 1, 4-Sept-2019
	Page: 8 of 15

statistics: number of observations, mean, median, standard deviation, minimum and maximum values. All analyses will be performed in SAS 9.4 or later.

7.2 Analysis Populations

Safety Population (SAF): all subjects who receive study treatment. This population include all enrolled subjects who receive the protocol-defined treatment of suture-based meniscal repair. This will be used for summaries of disposition of the subjects, protocol deviations/violations, and safety.

Analysis Population (AS): all SAF subjects with no significant protocol deviations, meet the inclusion/exclusion criteria, and did not withdraw early (except for closure at any time). This population will be used for supportive evidence of the primary variable.

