3.2. Rationale and Justification for the Study

a. Rationale for the Study Objectives

Although the clinical consensus holds that horizontal tears are often irreparable, there are no prospective, multi-center trials in the literature that document successful repair of the meniscus, surgical reoperation rates for meniscal tears and improvements in knee pain and function.

b. Rationale for Study Population

The study is limited to healthy subjects with horizontal meniscal tears. Although these injuries can occur in any age group, slightly younger age range (18-60 years of age) allows inclusion of knees with less likelihood of significant arthritic changes

which may mask measurement of knee pain and function improvements following the treatment procedure.

c. Rationale for Study Design

It is well established in the literature that meniscectomy leads to increased risk of late osteoarthritis, and conversely, that repairing the meniscus reduces this risk. The clinical consensus is that preservation of meniscal tissue should be the goal whenever possible. The alternative for these patients is meniscectomy (a failure endpoint in this study), therefore there is no available control. A prospective, non-randomized, single-arm assignment study design is the best method for obtaining objective data for clinicians and patients in weighing the viability of meniscal repair versus primary meniscectomy.

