5.3. Withdrawal Criteria

Subjects may withdraw from the study at any time prior to the subject’s expected completion and for any reason without prejudice to further treatment. Subjects considered treatment failures will be withdrawn from the study to receive appropriate alternative treatment.

A subject’s participation in the study may be discontinued at any time prior to the subject’s expected completion at the discretion of the Investigator or Sponsor. Reasons for removing a subject from the study include, but are not limited to, the following:

- The subject is uncooperative in adhering to the protocol requirements, including failure to participate in rehabilitation;
- The Investigator believes it is in the best interests of the subject;
- The subject withdraws consent.

The Investigator will attempt to document the subject’s reason for withdrawal on the study completion CRF.

If a subject fails to attend study visits, every attempt shall be made to contact the subject prior to considering the subject lost to follow up and withdrawing the subject from the study.

Subjects who are withdrawn from the study will not be replaced.

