9. STATISTICAL PLAN

9.1. Subject Population(s) for Analysis

Data obtained from all enrolled subjects will be analyzed on a per-treatment (PT) basis, which will include all enrolled subjects who receive the protocol-defined treatment of suture-based meniscal repair.

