7.3 Handling of Missing, Incomplete and Repeat Data

All data will be analyzed as observed cases unless otherwise indicated

CONFIDENTIAL AND PROPRIETARY

This document contains information that is confidential and proprietary to Smith & Nephew PLC and Smith & Nephew, Inc. and is intended for use only by Smith & Nephew and its manufacturer. It shall not be reproduced or copied in whole or in part, nor shall the contents be disclosed by any means without prior written permission from Smith & Nephew, nor shall anyone make any use of it that is contrary to the expressed or implied wishes of Smith & Nephew

Statistical Analysis Plan	Smith+Nephew
A Prospective, Non-randomized, Multi-Center Investigation of All-suture-based Repair of Horizontal Meniscal Tears (STITCH Study)	Number: CTX-CP001
	Version: 1, 4-Sept-2019
	Page: 9 of 15

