7.4 Derived Data

The study visits for this study are:

Stud Visit 1 = Screening visit

Study Visit 2 = Procedure visit

Study Visit 3 = Day 7-15

Study Visit 4 = Day 90

Study Visit 5 = Day 185

Study Visit 6 = Day 365

Study Visit 7 = Day 730

Analysis Populations

- Indicator for inclusion in the safety population.
- Indicator for inclusion in the analysis population.

Study Duration (will be calculated for each subject):

Study duration [days] = Date of study discontinuation – date of initial surgery

Freedom from reoperation of the index meniscus repair site (will be calculated at each visit):

Proportion of subjects with freedom from reoperation of the index meniscus repair site

$$= \frac{\text{Number of subjects whose known status were without repair}}{\text{Total number of participants with known repair status}} * 100\%$$

Change from pre-operative to post-operative visits in patient reported outcomes:

Change from pre- to post-operative visit will be calculated as:

Post – operative value_{Study Visit n} – Pre – operative value_(Study Visit 1), where n = 4,5,6,

Time since injury:

Time since injury will be calculated as:

Time since injury (in wk) = (Date of surgery – Date of injury)/7

CONFIDENTIAL AND PROPRIETARY

This document contains information that is confidential and proprietary to Smith & Nephew PLC and Smith & Nephew, Inc. and is intended for use only by Smith & Nephew and its manufacturer. It shall not be reproduced or copied in whole or in part, nor shall the contents be disclosed by any means without prior written permission from Smith & Nephew, nor shall anyone make any use of it that is contrary to the expressed or implied wishes of Smith & Nephew

Statistical Analysis Plan	Smith+Nephew
A Prospective, Non-randomized, Multi-Center Investigation of All-suture-based Repair of Horizontal Meniscal Tears (STITCH Study)	Number: CTX-CP001
	Version: 1, 4-Sept-2019
	Page: 10 of 15

Time to re-operation:

Time to reoperation will be calculated as:

Time to re-operation (in wk) = (Date of re-operation surgery – Date of original surgery)/7

Minimal clinically important differences (MCIDs):

- MCID-IKDC (Day185) Indicator = 1 if IKDC difference from baseline to Day 185 > 6.3,
= 0 otherwise;
- MCID-IKDC (Day 365) Indicator = 1 if IKDC difference from baseline to Day 365 > 16.7,
= 0 otherwise;
- MCID-Lysholm (Day365) Indicator = 1 if Lysholm difference from baseline to Day 365 > 10.1,
= 0 otherwise;

Adverse Events

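### The SAP names no main population for freedom from reoperation, and the only set it ties to the primary variable can drop subjects because they were reoperated

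*SAP*

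**What the plan says.** Protocol 9.1 sets one analysis population, "which will include all enrolled subjects who receive the protocol-defined treatment of suture-based meniscal repair".

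SAP 7.2 defines two. The SAF matches the protocol population, and its stated use is limited: "This will be used for summaries of disposition of the subjects, protocol deviations/violations, and safety". The AS is narrower: "all SAF subjects with no significant protocol deviations, meet the inclusion/exclusion criteria, and did not withdraw early (except for closure at any time". Of the AS the SAP says: "This population will be used for supportive evidence of the primary variable".

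SAP 7.9 plans the proportion free of reoperation at 6 months, 1 year and 2 years with an exact 95% interval, a summary of reoperations, and a logistic model for predictors. It names no population for any of them. The safety section, by contrast, does name its set.

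Two protocol statements bear on who leaves the AS. Section 5.3: "Subjects considered treatment failures will be withdrawn from the study to receive appropriate alternative treatment". Section 3.2c: "The alternative for these patients is meniscectomy (a failure endpoint in this study), therefore there is no available control".

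SAP 7.4 calculates the proportion at each visit, with the denominator "Total number of participants with known repair status". SAP 7.3 adds: "All data will be analyzed as observed cases unless otherwise indicated". SAP 6.1 reports that 30 subjects were accrued and that 3 were left out of every analysis because of protocol deviations.

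**The concern.** Freedom from reoperation is the first primary endpoint listed in SAP 5.1. The SAP supplies a supportive set for it but no main set for that analysis to support. The set that fits the protocol is defined and then not assigned to this endpoint.

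The AS has a problem of its own. It requires that a subject did not withdraw early, and under the protocol a failed repair is itself a reason for withdrawal. Membership of the set can therefore depend on the outcome that the set is used to estimate. If a larger share of reoperated than of event-free subjects is removed, the AS rate is too high.

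The study is descriptive and has no control group, so the proportion and its interval are the result. In a set of about 27 subjects, each reoperated subject left out moves the rate by about 3 points or more.

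**Working it through.** **Inputs.** From the documents: 30 accrued and 3 excluded (SAP 6.1), so 30 − 3 = 27; the proportion is subjects free of reoperation over subjects with known status (SAP 7.4); intervals are exact Clopper-Pearson 95% (SAP 7.9). The documents give no reoperation or withdrawal counts, so every count below is an assumption. There is no sample-size or rate calculation in the plan to reproduce.

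**Step 1: the text.** For the primary endpoint, the SAF is not assigned, the AS is assigned as supportive, and SAP 7.9 is silent. No main set follows. The route out of the AS is: reoperation (for example meniscectomy), failure (Protocol 3.2c), withdrawal (Protocol 5.3), not in the AS (SAP 7.2). Each link is permitted by the text. None is certain, because treatment failure is not defined and the exception for closure is not explained.

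**Step 2: effect on the AS rate.** Let r be reoperations among the 27, d the reoperated subjects dropped from the AS, and w the event-free withdrawals dropped.

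AS rate = (27 − r − w) / (27 − w − d)

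| Assumed r | w | d = 0 | d = 1 | larger d | all dropped (limit) |
|---|---|---|---|---|---|
| 6 | 0 | 21/27 = 77.8% | 21/26 = 80.8% | d = 3: 21/24 = 87.5% | 21/21 = 100% |
| 6 | 4 | 17/23 = 73.9% | 17/22 = 77.3% | d = 3: 17/20 = 85.0% | 17/17 = 100% |
| 3 | 0 | 24/27 = 88.9% | 24/26 = 92.3% | d = 2: 24/25 = 96.0% | 24/24 = 100% |
| 3 | 4 | 20/23 = 87.0% | 20/22 = 90.9% | d = 2: 20/21 = 95.2% | 20/20 = 100% |

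With nobody dropped, the exact 95% intervals are 57.7 to 91.4% for 21/27 and 70.8 to 97.6% for 24/27.

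**Step 3: when the two effects cancel.** Setting the AS rate equal to (27 − r)/27 gives w = (27 − r) × d / r. For r = 6 this is 21/6 = 3.5 event-free withdrawals per dropped reoperation. For r = 3 it is 24/3 = 8. The direction is upward unless event-free withdrawals exceed these numbers.

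**Step 4: which estimate to lead with.** Assume 30 treated, 2 reoperations in each of the three intervals, and 2 event-free subjects lost after 6 months and 2 more after 1 year. Failures are kept in the denominator.

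- Known-status proportion at 2 years: 20 free and 6 reoperated, 20/26 = 76.9%.
- Kaplan-Meier at 2 years: 28/30 × 24/26 × 20/22 = 78.3%.

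The known-status proportion is lower because it keeps every failure but discards the event-free time of those lost. Kaplan-Meier uses that time up to the loss.

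**Step 5: the 3 excluded subjects.** The 27 used in Step 2 is the full set only if those 3 do not belong to the SAF. If they do, and 21 of the other 27 are free of reoperation, the all-treated rate lies between 21/30 = 70.0% (all 3 reoperated) and 24/30 = 80.0% (none reoperated).

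**The case against.** The strongest reply is that the AS is only supportive, so its selection need not touch the main estimate, and that exclusion by event is an inference across three passages. Nothing states that a reoperated subject counts as an early withdrawal, and the exception for closure might cover some of these exits. SAP 7.9 also plans to describe time to reoperation and surgical details among reoperated subjects, so the plan expects to analyse them. This stands as a limit on size and certainty. It does not supply the missing main set, and it does not stop the AS rule from acting on the event.

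A reader might go further in four ways, none of which the documents support:

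- **That the AS is the primary set and will show 100%.** It is labelled supportive. The 100% column is a limiting case that needs every reoperated subject to be recorded as an early withdrawal.
- **That SAP 7.4 removes reoperated subjects from later denominators.** In the Step 4 example without other losses, that would give 24/26 = 92.3% instead of 24/30 = 80.0% at 2 years. But the denominator rests on known status, not on attendance. A recorded reoperation naturally stays known, time to reoperation is derived from dates, and SAP 7.9 also reports all reoperations. The gap is a missing sentence.
- **That the SAP departs from Protocol 9.1 without explanation.** Its contents list a section on changes from the protocol's methods. That section was not in the text available for this review, so the point is limited to 7.2 and 7.9.
- **That leaving out the 3 subjects breaks the protocol.** Protocol 6.2b enrols a subject when the repair is complete, but the definition of an enrolled subject also requires that the inclusion criteria were met. If the deviations were eligibility failures, these subjects may fall outside Protocol 9.1.

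**Conclusion.** The point holds in this form: in the available text, no main population is assigned to freedom from reoperation, and the supportive AS can exclude subjects because of the primary event, which can bias its rate upward. The first part is plain from SAP 7.2 and 7.9. The second is a possibility created by reading SAP 7.2 with Protocol 5.3 and 3.2c.

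The realised size cannot be known from the documents. In the main illustration (6 assumed reoperations among 27), dropping 1 to 3 reoperated subjects raises the rate by 3.0 to 9.7 points, which event-free withdrawals would partly or wholly offset. The point should be fixed; confidence is medium, because the gap is clear and its effect is not.

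**What to change.** 1. In SAP 7.2 and 7.9, name all treated subjects (the SAF, matching Protocol 9.1) as the main set for freedom from reoperation, the reoperation summary and the logistic model.
2. Keep the AS as a sensitivity set, and state that withdrawal because of reoperation or treatment failure excludes no one from it. This concerns the analysis set only, not how failures are managed.
3. Report Kaplan-Meier estimates at 6 months, 1 year and 2 years in the SAF, since the protocol synopsis makes a reoperation survival curve an objective. Say whether these or the known-status proportion lead, because the latter leans low when event-free subjects are lost.

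As clarifications only: state in SAP 7.4 that an index-site reoperation counts as a failure at that and every later time point; define closure in SAP 7.2; and reconcile SAP 6.1 with 7.2 by saying whether the 3 subjects were enrolled and received the repair the protocol defines, keeping them in the SAF if so.

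The cost is SAP wording and some re-run tables, with no new data. The reported rate may be less favourable.

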7.3 Handling of Missing, Incomplete and Repeat Data

All data will be analyzed as observed cases unless otherwise indicated

CONFIDENTIAL AND PROPRIETARY

This document contains information that is confidential and proprietary to Smith & Nephew PLC and Smith & Nephew, Inc. and is intended for use only by Smith & Nephew and its manufacturer. It shall not be reproduced or copied in whole or in part, nor shall the contents be disclosed by any means without prior written permission from Smith & Nephew, nor shall anyone make any use of it that is contrary to the expressed or implied wishes of Smith & Nephew

Statistical Analysis Plan	Smith+Nephew
A Prospective, Non-randomized, Multi-Center Investigation of All-suture-based Repair of Horizontal Meniscal Tears (STITCH Study)	Number: CTX-CP001
	Version: 1, 4-Sept-2019
	Page: 9 of 15

7.4 Derived Data

The study visits for this study are:

Stud Visit 1 = Screening visit

Study Visit 2 = Procedure visit

Study Visit 3 = Day 7-15

Study Visit 4 = Day 90

Study Visit 5 = Day 185

Study Visit 6 = Day 365

Study Visit 7 = Day 730

Analysis Populations

- Indicator for inclusion in the safety population.
- Indicator for inclusion in the analysis population.

Study Duration (will be calculated for each subject):

Study duration [days] = Date of study discontinuation – date of initial surgery

Freedom from reoperation of the index meniscus repair site (will be calculated at each visit):

Proportion of subjects with freedom from reoperation of the index meniscus repair site

$$= \frac{\text{Number of subjects whose known status were without repair}}{\text{Total number of participants with known repair status}} * 100\%$$

Change from pre-operative to post-operative visits in patient reported outcomes:

Change from pre- to post-operative visit will be calculated as:

Post – operative value_{Study Visit n} – Pre – operative value_(Study Visit 1), where n = 4,5,6,

Time since injury:

Time since injury will be calculated as:

Time since injury (in wk) = (Date of surgery – Date of injury)/7

CONFIDENTIAL AND PROPRIETARY

This document contains information that is confidential and proprietary to Smith & Nephew PLC and Smith & Nephew, Inc. and is intended for use only by Smith & Nephew and its manufacturer. It shall not be reproduced or copied in whole or in part, nor shall the contents be disclosed by any means without prior written permission from Smith & Nephew, nor shall anyone make any use of it that is contrary to the expressed or implied wishes of Smith & Nephew

Statistical Analysis Plan	Smith+Nephew
A Prospective, Non-randomized, Multi-Center Investigation of All-suture-based Repair of Horizontal Meniscal Tears (STITCH Study)	Number: CTX-CP001
	Version: 1, 4-Sept-2019
	Page: 10 of 15

Time to re-operation:

Time to reoperation will be calculated as:

Time to re-operation (in wk) = (Date of re-operation surgery – Date of original surgery)/7

Minimal clinically important differences (MCIDs):

- MCID-IKDC (Day185) Indicator = 1 if IKDC difference from baseline to Day 185 > 6.3,
= 0 otherwise;
- MCID-IKDC (Day 365) Indicator = 1 if IKDC difference from baseline to Day 365 > 16.7,
= 0 otherwise;
- MCID-Lysholm (Day365) Indicator = 1 if Lysholm difference from baseline to Day 365 > 10.1,
= 0 otherwise;

Adverse Events

- Individual flags for whether each adverse event was a new complication, a major complication (if answer was yes to at least one of the following: related to a fall or other injury, related to surgical procedure, related to meniscal repair, related to device(s) used, resolved, not resolved/ongoing, and/or death.
- The duration of adverse events defined as:
 - Duration of resolved AE (in day) = End date – start date
 - Duration of unresolved AE (in day) = Date of study completion – start date

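### Freedom from reoperation is a per-visit observed-case proportion rather than the survival estimate the protocol asks for, and the only population linked to it can drop failures

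*SAP*

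**What the plan says.** **What is asked for.** The protocol synopsis puts a survival curve for reoperation among the primary objectives. Protocol 4.1 names a two-year reoperation survival rate, to be set against historical rates. Protocol 4.3 and SAP 4 speak only of a reoperation rate.

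**What is estimated.** SAP 7.4 defines freedom from reoperation at each visit as "Number of subjects whose known status were without repair" divided by "Total number of participants with known repair status". SAP 7.3 adds: "All data will be analyzed as observed cases unless otherwise indicated". SAP 7.9 reports the proportion at 6 months, 1 year and 2 years with Clopper-Pearson intervals. Time to reoperation is summarised only among those who were reoperated.

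**Who is analysed.**
- Protocol 9.1: data "will be analyzed on a per-treatment (PT) basis, which will include all enrolled subjects who receive the protocol-defined treatment".
- SAP 7.2, Safety Population: "This population include all enrolled subjects who receive the protocol-defined treatment of suture-based meniscal repair". It is assigned to disposition, deviations and safety.
- SAP 7.2, Analysis Population: treated subjects without significant deviations who met the criteria and "did not withdraw early (except for closure at any time). This population will be used for supportive evidence of the primary variable".
- SAP 6.1: 3 subjects are left out of every analysis because of protocol deviations.

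**What happens to failures.** Protocol 5.3: "Subjects considered treatment failures will be withdrawn from the study to receive appropriate alternative treatment". Protocol 3.2c: "The alternative for these patients is meniscectomy (a failure endpoint in this study), therefore there is no available control".

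**The concern.** There are two problems of unequal weight.

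The lesser one is the estimator. A stated objective has no visible analysis, and the event-free follow-up time of subjects who are later lost is not used.

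The greater one is the population. If a reoperated subject is judged a treatment failure and withdrawn, the early-withdrawal exclusion takes that subject out of the data that measure failure, and the result moves in favour of the procedure. The SAP names no other population for this endpoint, does not say that a reoperated subject stays a failure at later visits, and does not explain the exception for closure. This departs from Protocol 9.1, whose all-treated definition SAP 7.2 gives to the Safety Population. Leaving 3 subjects out of all analyses departs from it too, if they were treated.

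This is the main durability result of a single-arm study without formal hypotheses, so sound description is what it has to deliver. The formula also needs a correction: its numerator counts subjects without repair, yet every enrolled subject had a repair, and reoperation is meant.

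**Working it through.** The plan has no figure to reproduce: SAP 6.1 states that no sample size calculation was made, and neither document gives a reoperation or loss rate.

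**Inputs from the documents:** 30 enrolled and 3 excluded (SAP 6.1), hence 27 if the 3 are among the 30; 2-year follow-up. **Everything else is assumed.**

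**Step 1. Bias from event-free losses.** On the natural reading a documented reoperation stays known; the regression and the reoperation count in SAP 7.9 presuppose this. Failures then stay in the denominator while event-free losses leave it. Let F be the 2-year reoperation risk and L the 2-year loss, both with exponential times. With λ = −ln(1−F), μ = −ln(1−L) and N = (1−F)(1−L):

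crude freedom = N / [N + (λ/(λ+μ))·(1−N)]

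Example, F = L = 0.20: N = 0.64 and λ/(λ+μ) = 0.5, so crude = 0.64/(0.64 + 0.18) = 78.0% against a true 80%.

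| True freedom | L = 10% | L = 20% | L = 30% |
|---|---|---|---|
| 90% | 89.5% (−0.5) | 88.9% (−1.1) | 88.2% (−1.8) |
| 80% | 79.1% (−0.9) | 78.0% (−2.0) | 76.8% (−3.2) |
| 70% | 68.8% (−1.2) | 67.4% (−2.6) | 65.8% (−4.2) |

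The bias runs against the procedure, is zero with full follow-up, and is small beside the confidence interval.

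**Step 2. Kaplan-Meier in an assumed case.** n = 27, reoperations at months 3, 7, 11, 15 and 20, event-free losses at months 5, 9, 14 and 18. Numbers at risk at the five events are 27, 25, 23, 21 and 19:

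S(24) = (26/27)(24/25)(22/23)(20/21)(18/19) = 79.8%

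The Greenwood log-log 95% CI is 57.9–91.1%. The estimate is 96.3% at 6 months and 88.4% at 12 months. At 24 months it would be 78.3% with all losses before the events and 81.5% with all after. The SAP proportion with failures kept is 18/23 = 78.3% (exact 95% CI 56.3–92.5%).

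**Step 3. Early-withdrawal exclusion.** In the same case the 4 losses are removed, and k of the 5 reoperated subjects are removed as early withdrawals. The proportion is 18/(23−k).

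| k | Proportion | Exact 95% CI | Shift from 78.3% |
|---|---|---|---|
| 0 | 18/23 = 78.3% | 56.3–92.5 | 0 |
| 1 | 18/22 = 81.8% | 59.7–94.8 | +3.5 |
| 2 | 18/21 = 85.7% | 63.7–97.0 | +7.4 |
| 3 | 18/20 = 90.0% | 68.3–98.8 | +11.7 |
| 4 | 18/19 = 94.7% | 74.0–99.9 | +16.4 |
| 5 | 18/18 = 100% | 81.5–100 | +21.7 |

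A second assumed case (n = 27, 5 reoperated, 3 lost, times evenly spread) behaves the same way. Kaplan-Meier is 80.3% (58.9–91.3). The proportion is 19/24 = 79.2% with all failures kept, 19/22 = 86.4% with two dropped and 19/19 = 100% with all dropped.

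**Step 4. The 3 excluded subjects.** Add them back to the step 2 case (n = 30) with r of them reoperated, at months 6.5, 12.5 and 18.5 in turn, and the others event-free to month 24.

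| r | Kaplan-Meier (95% CI) | Shift from 79.8% | Proportion, failures kept |
|---|---|---|---|
| 0 | 82.0% (61.9–92.1) | +2.2 | 21/26 = 80.8% |
| 1 | 78.5% (58.1–89.8) | −1.3 | 20/26 = 76.9% |
| 2 | 74.9% (54.3–87.2) | −4.9 | 19/26 = 73.1% |
| 3 | 70.9% (50.0–84.3) | −8.8 | 18/26 = 69.2% |

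Shifts are taken before rounding. For r = 3, Kaplan-Meier would be 71.8% with all three events at month 1 and 70.3% with all at month 23.

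**The case against.** The endpoint is defined at fixed times, Protocol 4.3 and SAP 4 ask for a rate, and Protocol 9.2 plans descriptive statistics for it. A proportion with an exact interval meets that wording, and its bias from losses is small and conservative. The Analysis Population is labelled supportive, which implies a main analysis elsewhere, and Protocol 9.1 says where. For a failure to be deleted, four things must hold: the reoperated subject is judged a treatment failure (a term the protocol does not define), is withdrawn, counts as withdrawn early, and is not saved by the closure exception. SAP 7.9 plans a series of descriptors for reoperated subjects, which would be empty if all of them were removed. All counts above are assumed. The SAP contents also list a section on changes from the protocol's methods that was not in the text available, and the table and figure shells are a separate document.

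Much of this stands. The estimator alone would be a minor point, the 100% row is a limiting case, and nothing suggests that all 3 excluded subjects were reoperated. But the synopsis and Protocol 4.1 still call for a survival estimate, so the objectives need reconciling. The supportive label does not supply the missing main population. Removing even one or two failures matters, and nothing visible in the SAP prevents it.

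**Conclusion.** The concern holds and should be fixed. The visible SAP provides no survival curve or survival estimate, and it links the primary variable only to a population whose early-withdrawal rule can remove failures.

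Whether that happens depends on how reoperated subjects are handled. If none is withdrawn, the exclusion has no effect. In the assumed case each withdrawn failure adds about 3.5 to 5.3 points, up to 21.7 if all five are withdrawn. The choice between proportion and Kaplan-Meier moves the same case by 1.5 points (79.8 − 78.3). Whether the 3 excluded subjects are counted moves Kaplan-Meier by +2.2 to −8.8 points, depending on their outcomes.

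The direction of the population effect follows from the text. Its size rests on assumed counts, so confidence is medium. The unseen section on changes, or the shells, might already settle part of it.

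**What to change.** In SAP 7.4 and 7.9:

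- Make the main analysis Kaplan-Meier estimates at 6, 12 and 24 months with 95% CIs, the curve and numbers at risk, in all treated subjects (the Safety Population, in line with Protocol 9.1).
- Count any reoperation at the index repair site as an event from its date, whether or not the subject is then withdrawn. Do not apply the early-withdrawal exclusion to this endpoint.
- Censor all others at the last date with known status.
- Reconcile with SAP 6.1 by showing the result with and without the 3 excluded subjects.
- Keep the Clopper-Pearson proportion, with failures carried forward, as a companion and as the interval if there are no events (27/27: 87.2–100%; 30/30: 88.4–100%).
- Correct the numerator to refer to reoperation.

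Best- and worst-case bounds and a sensitivity analysis on treatment failure are optional.

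**Cost:** SAP wording, one table, one figure and one new derived date, taken from the safety follow-up visits; SAP 7.4 already uses the surgery and reoperation dates. The with-and-without display needs the reoperation status of the 3 excluded subjects. The drawback is that the Kaplan-Meier interval is asymptotic at 27 to 30 subjects and assumes non-informative loss, which is why the exact companion stays.
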